Approval Date: 21st November, 2022

**DOES PERI-OPERATIVE PARENTERAL NUTRITION
AFFECT OUTCOME IN PATIENTS UNDERGOING MAJOR
ABDOMINAL SURGERIES**

NEPAL MEDICAL COLLEGE

SUBMITTED BY

[name]. [name]

Head of Department

Department of Surgical Gastroenterology

Nepal Medical College, [name]

RESEARCH DESIGN:

Type of study: Retrospective observational study

Place of study: Department of Surgical Gastroenterology, Nepal Medical College and Teaching Hospital, [name].

Duration of study: 2017, January 1st to 2022, August 31st (5 years 7 months)

Sampling technique: Consecutive sampling technique

Sample Size:

To select the appropriate sample size, we considered the prevalence of malnutrition in surgical patients to be 24% (3) at a confidence interval of 95% ($Z = 1.96$), and a precision (d) of 7%. Based on these calculations, the sample size obtained was 143.

We obtained the sample size using the following formula:

For large population (infinite population)

$$= 3.84 * 0.24 * 0.76 / (0.07 * 0.07) = 142.9 = 143$$

n = Sample size

$$Z^2 = 1.96 * 1.96 = 3.84$$

$$p = \text{Prevalence value} = 24\% = 0.24$$

$$q = 1 - p = 1 - 0.24 = 0.76$$

$$d = \text{desirable error or precision level (5% to 10\%)} = 7\% = 0.07 \text{ (pre-set value)}$$

Inclusion criteria:

1. All patients who underwent major gastrointestinal surgery after receiving perioperative TPN.

Exclusion criteria:

1. Patient refused to participate.
2. Perioperative TPN was not given as per the protocol.

Ethical consideration:

All patients enrolled in the study were explained about the enrollment, and verbal and written consent were obtained from the patient. Patients were counseled about the strict confidentiality that would be maintained throughout their participation in this study, and that their name would not be disclosed in the proforma or after the completion of study until voluntarily disclosed by the patient. Ethical approval will be obtained from the Institutional Review Committee (IRC) of Nepal Medical College and Teaching Hospital.

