Data collection: All patients that undergo major gastroenterological surgeries are always entered in our data sheet maintained by the department. As all the data regarding the hospital stay, course of illness, management and operation procedures are clearly maintained in these data sheets, we will only select those cases who received perioperative TPN. A sample of this data sheet which is also our proforma is shown in Annex I.

Study Procedure:

1. Consent: After obtaining ethical clearance from the IRC, those patients that fulfill the inclusion criteria will be offered detailed printed information about the proposed study. Since this is a retrospective study, phone calls will be done to the patients and their relatives for consent. Patients agreeing to take part in the study will be requested to sign the consent form. After signing the consent, the patient's data will be recruited in this study. There will be no discrimination of sex, race, religion and geography.

2. Nutritional status assessment: All the patients were evaluated for nutritional status by following the ESPEN guidelines¹⁰ at the time of admission. According to the guidelines, the diagnosis of malnutrition is based on two options:

(1) $\text{BMI} < 18.5 \text{ kg/m}^2$,

(2) Combined:

- Weight loss $>10\%$ indefinite of time or $>5\%$ over 3 months and
- Either reduced BMI ($<20 \text{ kg/m}^2$ in younger than 70 or $<22 \text{ kg/m}^2$ in patients older than 70 years) or fat free mass index (FFMI) < 15 in women and 17 in men.

Similarly patients at severe nutritional deficiency risk are defined by presence of one of the following:

(1) Weight loss $>10\text{--}15\%$ within 6 months,

(2) $\text{BMI} < 18.5 \text{ kg/m}^2$, and

(3) Preoperative serum albumin $< 30 \text{ g/L}$ (without evidence of liver or kidney dysfunction).

3. Routes and selection of PN: All the patients who were found to have malnutrition or were at severe risk of nutrition deficiency were given preoperative PN. PN was given as infusion via central venous catheter from the day of admission via central venous catheter.¹¹ The CVC was kept by the anesthesiology team on the day of admission. The PN was available in a standard 3-compartment package developed by BAXTER and comprising lipid, carbohydrate and amino acids with minerals.

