4. Duration and dosing of PN: In those patients who required emergency surgery, PN was given in postoperative period until resumption of oral feeding. In non-emergent cases where surgery could be delayed for 5 days, PN was given for 5 days preoperatively based on the fact that our body needs at least 5-7 days to recover its full physiological activity and body protein framework and was continued in the post-operative period until the resumption of enteral feeding. The dosing of PN was based on ESPEN guidelines with total energy of 25-30Kcal/kg/day and 1.2g/kg/day of proteins.
5. Intraoperative and postoperative status: All patients underwent surgery after preoperative assessment on 5th day onwards of admission. All the surgeries were done by the same team of surgeons. The intraoperative events were recorded by taking in consideration the anesthesiology chart. Postoperatively their progress as well as outcome were filled in the datasheet everyday till discharge.
6. Complications: The complications faced by the patient were graded according to the Clavien-Dindo Classification system¹² by keeping records till 30 days of the surgical procedure date.

Data Analysis Technique: Data collected on a hard copy proforma will be entered and analyzed in Microsoft excel and into IBM- Statistical Package for the Social Sciences (SPSS) version 16.0 respectively. Continuous variables will be expressed as the mean value + or - standard deviation (SD) and range, while categorical variables will be expressed as proportions. We will use the chi-square test and the exact test of Fischer for analysis of categorical data and univariate

linear regression analysis to show association. The data, after analysis, will be reported with descriptive statistics, with all data reported as mean \pm SD, and the final result will be compared with various studies listed in the Literature Review section. Various frequency tables, charts, graphs, trends, plots and bar diagrams will be used to present the data.

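### If the nutritional markers that bring patients into this PN-only cohort are tested against outcome one at a time, the entry rule distorts the results, so they should be modelled together

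*Combined protocol and SAP*

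**What the plan says.** Four parts of the combined protocol and SAP matter here.

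- **Who is in the study.** The inclusion criterion is "All patients who underwent major gastrointestinal surgery after receiving perioperative TPN", and Data collection adds "we will only select those cases who received perioperative TPN". There is no group without PN.
- **Who received PN.** Study Procedure item 3: "All the patients who were found to have malnutrition or were at severe risk of nutrition deficiency were given preoperative PN".
- **What those states mean.** In item 2, "the diagnosis of malnutrition is based on two options": low BMI alone, or weight loss combined with either a reduced BMI (cut-off depending on age) or a low FFMI (cut-off depending on sex). Then "patients at severe nutritional deficiency risk are defined by presence of one of the following": weight loss, BMI below 18.5, or albumin below 30 g/L, the last counting only "without evidence of liver or kidney dysfunction".
- **How association is analysed.** Data Analysis Technique gives chi-square and Fisher tests for categorical data and a univariate "linear regression analysis to show association". It names no predictor, no outcome and no multivariable model.

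Item 4 says that emergency patients received PN after surgery. It does not say whether the item 3 rule selected them.

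**The concern.** A patient who entered by this rule with normal albumin must have qualified on BMI or weight loss, and the same holds the other way round. Selection therefore pushes the markers towards an inverse relation inside the cohort, even if they are unrelated among surgical patients in general. A one-at-a-time analysis then mostly compares patients deficient in one marker with patients deficient in another. The inclusion rule does this without any outside confounder.

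At stake is a report that low albumin or low BMI does not matter, or even protects, when the pattern comes from how patients entered. Data Analysis Technique also intends to compare the final result with published studies, whose patients may not have been selected in this way.

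**Working it through.** **The plan's own figure.** n = Z²pq/d² = 3.84 × 0.24 × 0.76 / 0.07² = 0.7004 / 0.0049 = 142.9, so 143. It reproduces. It is a precision figure for one prevalence and says nothing about associations.

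**Inputs.** The either/or rule, the PN-only restriction and the univariate model are in the documents. Marker prevalences, baseline risks, true effects and correlations are not; those below are assumptions, varied over a range.

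**Step 1: two independent markers A and B, baseline risk 20% (odds 0.25), true odds ratio (OR) 2 each, each abnormal in 30%.**
- One marker abnormal: odds 0.5, risk 0.333. Both abnormal: odds 1, risk 0.5.
- A abnormal: risk = 0.3 × 0.5 + 0.7 × 0.333 = 0.383, odds 0.622.
- A normal, all surgical patients: risk = 0.3 × 0.333 + 0.7 × 0.2 = 0.24, odds 0.316. Crude OR = 0.622 / 0.316 = 1.97.
- A normal, in the cohort: B must be abnormal, so odds 0.5. Crude OR = 0.622 / 0.5 = 1.24.
- At 15% prevalence the cohort OR is 1.12. If B has OR 3, it is 0.94 (30%) or 0.79 (15%).

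**Step 2: three independent markers, 9% each, baseline risk 15%.** The share meeting the rule is 1 − 0.91³ = 24.6%, close to the plan's 24%. Crude ORs by exact enumeration; joint ORs by simulation within the cohort.

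| True ORs | Crude, all surgical patients | Crude, cohort | Joint model, cohort |
|---|---|---|---|
| 2 / 2 / 2 | 1.98 each | 1.11 each | 1.94 / 1.94 / 1.97 |
| 1.5 / 2 / 3 | 1.48 / 1.96 / 2.96 | 0.70 / 1.03 / 1.86 | 1.50 / 2.01 / 2.97 |
| 2 / 1 / 1 | 2.00 / 1.00 / 1.00 | 2.00 / 0.72 / 0.72 | 1.99 / 0.99 / 0.98 |

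A sole causal marker is unbiased, while the null markers look protective. If no marker has an effect there is no bias.

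**Step 3: correlated markers (9% each, true OR 2 each).**

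| Latent correlation | Crude, all surgical patients | Crude, cohort |
|---|---|---|
| 0.3 | 2.34–2.40 | 1.23–1.27 |
| 0.6 | 3.08–3.12 | 1.52–1.55 |
| 0.8 | 4.05–4.09 | 1.86–1.90 |

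The joint model stayed between 1.94 and 2.04. With true ORs 1.5/2/3, the weakest marker reverses at correlation 0.3 (0.84) but not at 0.6 (1.09) or 0.8 (1.38).

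**Step 4: continuous markers, linear regression on length of stay.** Assumed: BMI N(22.5, 3.5), weight loss N(4, 5) floored at 0, albumin N(36, 5.5); entry if BMI <18.5, loss >10 or albumin <30; true joint slopes −0.25 (BMI), +0.20 (weight loss) and −0.25 (albumin); residual SD 6.

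| Correlation between deficits | Univariate BMI slope | Univariate albumin slope |
|---|---|---|
| 0 | −0.08 | −0.16 |
| 0.5 | −0.26 | −0.25 |
| 0.7 | about −0.4 | −0.32 |

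The joint model returned about −0.25 for both at every correlation tried. So, measured against the joint effect, the univariate slope can be too small, about right or too large.

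**Step 5: entry outside the rule.** In the first row of Step 2, the cohort OR of 1.11 becomes 1.32 if 20% of recipients fall outside the rule, and 1.67 if 50% do. In Step 4, 30% outside with correlation 0.3 gives slopes of −0.35 (BMI) and −0.30 (albumin).

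**The case against.** The strongest reply is that the criticised analysis is not in the plan. No predictor is named, and the title asks whether PN affects outcome, not which marker predicts it. That stands, and the point is therefore conditional. But BMI, weight loss, FFMI and albumin are the main quantitative baseline measures the text defines, so they are natural candidates for a regression meant to show association. A statement that they will not be tested would settle the matter.

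Three stronger readings are tempting, and the documents do not support them.

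- *The bias always runs towards no association.* Steps 2 and 4 show otherwise, and the documents give no marker correlations. Item 2 itself ties weight loss to BMI, so independence cannot be presumed.
- *A joint model gains power.* Under independence, simulated power for albumin at n=143 is about 46% univariate against 75% joint. At correlation 0.5 it is 63% against 63%, and at 0.7 it is 70% against 48%. Power is no argument for the change.
- *No well-nourished patient is in the cohort.* Item 3 says all malnourished or at-risk patients received PN, not that only they did, and the route of emergency patients is not described.

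Two further replies stand in part. At n=143 the reversals in Step 1 would be imprecise: OR 0.94 has an approximate 95% interval of 0.48 to 1.84, and OR 0.79 one of 0.41 to 1.55. A confident claim of protection is thus unlikely; a finding read as no effect is the more likely harm. And as a plain description of PN recipients, a univariate association is not wrong. The error lies in reading it as the marker's effect or comparing it with cohorts selected differently.

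**Conclusion.** The concern holds conditionally. The either/or entry rule, the restriction to PN recipients and the univariate-only model are all in the document. If the entry markers are tested one at a time, the results are distorted: attenuated (2 to roughly 1.1–1.4 with independent markers of equal effect), reversed for the weaker marker, falsely protective for a null marker, or exaggerated relative to the joint effect when the markers are strongly correlated. Neither direction nor size can be fixed from the documents, because both depend on the marker correlations and on the share of patients who entered outside the rule.

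A joint model recovered the assumed effects in every scenario tried. That rests on entry depending only on variables in the model, on an adequate model form, and on no interaction between markers. The change is worth making because it is cheap and better suited to this cohort than the univariate model.

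**What to change.** In Data Analysis Technique:

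1. Name the outcome or outcomes, and say whether nutritional markers will be analysed against them.
2. Where they are, enter BMI, percentage weight loss and admission albumin (and FFMI if recorded) together, as continuous values, in one model per outcome: linear for continuous outcomes, logistic for complications.
3. Include age, sex, liver or kidney dysfunction and emergency status in the same model. The first three enter the item 2 definitions, and emergency status may mark a different route into the cohort. State how emergency patients came to receive PN.
4. Show univariate results as description only, not as evidence of no effect or of protection.
5. Limit conclusions to PN recipients.

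**Cost.** This is mainly analysis wording. Whether every value was recorded cannot be confirmed, because the Annex I data sheet is not in the supplied text; missing markers need a stated rule. Intervals will widen if the markers are strongly correlated. Without FFMI the model has seven slopes. If 20% to 40% of 143 patients have the complication outcome (an assumption), that is about 29 to 57 events, or roughly 4 to 8 per slope. The logistic model may therefore need a penalised fit, or a shorter covariate list with the reason given.

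### Associations in this retrospective cohort rest on crude methods only: no recorded outcome is tied to a test or predictor, and no adjusted or stratified estimate is planned

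*Combined protocol and SAP*

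**What the plan says.** The combined protocol and SAP gives the design as "Type of study: Retrospective observational study". Under Data collection it adds "we will only select those cases who received perioperative TPN", so there is no group without parenteral nutrition (PN).

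The inferential plan is a single sentence under Data Analysis Technique: "We will use the chi-square test and the exact test of Fischer for analysis of categorical data", followed by univariate "linear regression analysis to show association". The word univariate stands directly before that last phrase. It may mean one predictor at a time or one dependent variable; on either reading no covariate is given.

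Two outcomes are recorded elsewhere. Study Procedure item 6 grades complications by Clavien-Dindo up to 30 days after surgery, and Data collection says hospital stay is held on the department's data sheet. Neither is linked to a test or a predictor.

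The plan also describes patient characteristics that matter here. Item 2 says "All the patients were evaluated for nutritional status by following the ESPEN guidelines", at admission. Item 3 says "All the patients who were found to have malnutrition or were at severe risk of nutrition deficiency were given preoperative PN". Item 4 makes the timing of PN depend on whether surgery was an emergency.

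**The concern.** In a non-randomised cohort, a characteristic can appear related to complications or hospital stay only because it is more common in sicker patients. Nutritional status is an obvious candidate: it is assessed at admission, steers PN treatment and may itself bear on outcome. Urgency is another, if emergency cases are in the cohort. With crude tests alone, a reader could take such an association for a risk factor and would have no adjusted estimate to set beside it.

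A second limit concerns the title, which asks whether PN affects outcome. Every included patient received PN, so no comparison inside the cohort answers that question, adjusted or not. The analysis section does not say so.

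**Working it through.** **1. The plan's own figure.** n = Z²pq/d² = 3.84 × 0.24 × 0.76 / 0.07² = 0.700416 / 0.0049 = 142.94, which rounds to the stated 143. The figure reproduces. It is a precision target for the prevalence of malnutrition and carries no power or effect size for an association. I use 143 below as the cohort size.

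**2. Can the bias be derived?** No. The documents give no complication rate, no predictor and no emergency share. Everything in steps 3 to 6 other than n is assumed, and a range is shown.

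**3. Binary outcome, predictor with no true effect.** Let a share s of the cohort be in the worse stratum, with predictor prevalence p1 there and p0 elsewhere, and complication risk r1 there and r0 elsewhere. Then:

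- P(worse | predictor present) = s·p1 / [s·p1 + (1−s)·p0]
- P(worse | predictor absent) = s(1−p1) / [s(1−p1) + (1−s)(1−p0)]
- crude risk in each predictor group = r0 + (r1 − r0) × P(worse | group)

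Example (nutrition, middle case): s = 0.5, p1/p0 = 50%/30%, r1/r0 = 40%/25%. P(worse) is 0.25/0.40 = 0.625 with the predictor and 0.25/0.60 = 0.4167 without. The risks are 0.25 + 0.15 × 0.625 = 0.3438 and 0.25 + 0.15 × 0.4167 = 0.3125. The crude odds ratio is (0.3438/0.6562)/(0.3125/0.6875) = 1.152, although the odds ratio within each stratum is 1.

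False-positive rates at the 5% level, from 60,000 simulated cohorts of 143 per scenario:

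| Assumed confounder | Risk r1/r0 | Predictor p1/p0 | Crude OR | Chi-square | Fisher |
|---|---|---|---|---|---|
| Nutrition, half worse | 35/25% | 45/35% | 1.051 | 5.3% | 4.2% |
| Nutrition, half worse | 40/25% | 50/30% | 1.152 | 7.1% | 5.8% |
| Nutrition, half worse | 45/20% | 50/30% | 1.266 | 10.2% | 8.6% |
| Urgency, 5% share | 50/25% | 60/30% | 1.088 | 5.7% | 4.6% |
| Urgency, 10% share | 50/25% | 60/30% | 1.164 | 7.2% | 5.9% |
| Urgency, 30% share | 50/25% | 60/30% | 1.349 | 13.3% | 11.4% |

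Adjusting for or stratifying on the confounder brings the rate back to about 5% (4.7% to 5.2%).

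**4. Continuous outcome (hospital stay).** Bias = shift × (0.625 − 0.4167) = 0.208 × shift. If worse nutrition adds 0.2, 0.3 or 0.5 SD, the bias is about 0.042, 0.063 or 0.104 SD. Crude linear regression then rejects in 5.7%, 6.6% or 8.8% of cohorts, against about 5.0% adjusted.

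**5. How much adjustment the data could carry.** At an assumed 10 events per model term, complication rates of 10%, 20% and 30% give 143 × rate = 14, 29 and 43 events, or 1, 2 and 4 terms including the predictor. At 10% there is no room for a covariate.

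**6. Cost of adjusting.** With a nutrition odds ratio of 2 and a 50%/30% predictor, one covariate raises the standard error of the log odds ratio as follows:

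- 28.6 events: 0.436 to 0.451 (+3.4%)
- 42.9 events: 0.377 to 0.392 (+4.0%)
- 63.0 events: 0.348 to 0.364 (+4.6%)

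At 28.6 events the 95% limits move from ×/÷ exp(1.96 × 0.436) = 2.35 to ×/÷ exp(1.96 × 0.451) = 2.42. Three covariates cost +11.9% in one assumed case (0.394 to 0.441). For hospital stay the rise is at most 0.172 to 0.175, under 2%.

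**The case against.** The strongest reply is that little consequence has been shown. Every input is assumed, and the mildest nutrition case shows almost no inflation. Fisher's exact test, which the plan also lists, falls below 5% there and in the 5% urgency case. Because item 3 directs preoperative PN to malnourished or severely at-risk patients, the nutritional range may be narrow, which favours the low end. This stands, and it is why the size is called modest.

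The plan is also largely descriptive: "The data, after analysis, will be reported with descriptive statistics, with all data reported as mean" with SD, then compared with published work. It promises no independent predictors. That weakens the point without removing it, because the regression is there expressly to show association and the title asks about an effect.

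Part of the source is not visible. Annex I and the Literature Review may state objectives or list variables, so the finding is limited to the supplied text. A list of collected fields would not in itself be an analysis plan.

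Adjustment has limits too. The simulated adjusted rates assume one perfectly measured binary confounder. A single measure such as BMI would miss patients who qualify through weight loss or albumin under item 2, so some confounding would remain. That argues for using nutritional status as assessed at admission, not for leaving it out.

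A reader might infer that the plan names no outcome at all. It does record complications and hospital stay; what is missing is the link from an outcome to a test and a predictor.

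**Conclusion.** The point holds in a limited form. Followed as written, the supplied text yields crude within-cohort associations only, and these may be confounded by nutritional status. With nutrition as confounder, chi-square false-positive rates of about 5% to 10% are plausible under the assumed inputs, against about 5% adjusted. The true size is unknown and probably modest. This is a cheap improvement, not a defect that invalidates the study.

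Three stronger readings are not supported:

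- **That urgency confounds the results.** The 13.3% figure needs 30% emergency cases, and whether there are any is unsettled. Item 4 describes postoperative PN for emergency surgery, item 5 has all patients operated on from the fifth day of admission, and the inclusion criterion requires surgery to follow TPN.
- **That the associations are known to be seriously biased.** No figure in the documents allows that conclusion.
- **That adjustment would answer the title question.** Without patients who did not receive PN, it cannot.

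The same paragraph also conflicts with itself in applying mean and SD to all data when it has just said "while categorical variables will be expressed as proportions". That is a separate reporting matter and adds no weight here.

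**What to change.** Reword the Data Analysis Technique section as follows.

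1. For each association, report the crude estimate and one adjusted for a short pre-set list of recorded baseline variables. Nutritional status as assessed at admission comes first, unless it is the predictor under study. Let the observed events limit the number of terms. Where events are too few, label the association unadjusted and exploratory.
2. For a binary outcome, such as any complication within 30 days, use logistic regression with odds ratios and 95% confidence intervals. Keep linear regression for continuous outcomes such as hospital stay.
3. State that, because every included patient received PN, no within-cohort association, crude or adjusted, estimates the effect of PN asked about in the title.
4. Before adding an urgency term, reconcile Study Procedure items 4 and 5 with the inclusion criterion.

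The cost is one reworded section, a little more analysis and the slightly wider intervals shown in the working. Nutritional status should already be available for all patients. Whether other covariates such as age or urgency are recorded cannot be seen, because Annex I is not in the supplied text.

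### No confidence interval is planned for any outcome, yet the result is compared with published studies, so chance and case-mix differences could be read as an effect of parenteral nutrition

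*Combined protocol and SAP*

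**What the plan says.** Under Data Analysis Technique, "Continuous variables will be expressed as the mean value + or - standard deviation (SD) and range", while "categorical variables will be expressed as proportions". "The data, after analysis, will be reported with descriptive statistics", and then "the final result will be compared with various studies listed in the Literature Review section". No outcome, target study, measure of difference or matching rule is named for that comparison.

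The same section also names inferential methods: "We will use the chi-square test and the exact test of Fischer for analysis of categorical data", and univariate "linear regression analysis to show association". Neither the groups nor the outcomes for these are stated, and nothing links them to the comparison with the literature.

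The only reference to 95% confidence is under Sample Size, where the calculation is made "at a confidence interval of 95" percent with a precision of 7 points. Its target is the prevalence of malnutrition, taken as 24%, and not an outcome rate.

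Data collection restricts the cohort to patients who received perioperative TPN. Study Procedure item 4 describes two regimens. For emergencies, "In those patients who required emergency surgery, PN was given in postoperative period until resumption of oral feeding". Where surgery could wait, PN was given for 5 days beforehand and continued afterwards. No reporting by emergency status is specified.

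**The concern.** The title asks whether perioperative PN affects outcome. With no patients outside the PN group, the study itself cannot contrast PN with its absence, and whatever is said on the title question will lean on the comparison with published studies. That step has no stated method and no measure of uncertainty. SD and range describe how patients vary; they do not say how precisely a rate or a mean has been estimated.

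Two things other than PN can separate this cohort's rate from a published one. One is sampling error, in both studies. The other is case mix, including the share of emergency patients if they are in the cohort. Bare point estimates show neither. At stake is an unsupported statement that outcomes with PN are better or worse than elsewhere.

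**Working it through.** **Inputs from the documents.** Planned n = 143; Z = 1.96; assumed malnutrition prevalence 0.24; precision 0.07.

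**Assumptions.** The documents give no expected outcome rate, no emergency share and no rates by emergency status. The Literature Review is not in the text available, so the comparator size m is unknown too. I use outcome rates of 10% to 40% and m = 50, 100 and 200.

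**1. The plan's own figure.** n = Z²pq/d² = 3.84 × 0.24 × 0.76 / 0.07² = 142.9, rounded to 143. It reproduces. It concerns prevalence, so it does not assure precision for any outcome.

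**2. Precision of an outcome at n = 143.** The simple half-width is 1.96 × √(p(1−p)/143). The Wilson interval has centre (p + z²/2n)/(1 + z²/n) and half-width z√(p(1−p)/n + z²/4n²)/(1 + z²/n).

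| Assumed rate | Events | Simple half-width (points) | 95% Wilson interval |
|---|---|---|---|
| 10% | 14 | 4.9 | 5.9% to 15.8% |
| 20% | 29 | 6.6 | 14.5% to 27.6% |
| 30% | 43 | 7.5 | 23.2% to 38.0% |
| 40% | 57 | 8.0 | 32.2% to 48.0% |

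For 43/143 = 0.3007, the Wilson centre is 0.306 and the half-width 0.074. With no events at all, the exact upper limit is 1 − 0.025^(1/143) = 2.5%. For a mean, the half-width is 1.96/√143 = 0.164 SD.

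**3. Gaps that arise by chance.** Suppose this cohort and a published study of size m share the same true rate p. The standard error of the difference is √(p(1−p)(1/143 + 1/m)). At p = 0.30 and m = 100 it is √(0.21 × (0.00699 + 0.01)) = 0.0597, so 95% of chance differences lie within ±1.96 × 0.0597 = ±11.7 points. The probabilities below sum the exact binomial distributions of the two samples.

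| True rate in both | m | Gap of 5 points or more | Gap of 10 points or more |
|---|---|---|---|
| 30% | 50 | 50% | 19% |
| 30% | 100 | 40% | 9% |
| 30% | 200 | 32% | 5% |
| 10% | 100 | 20% | 1% |

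**4. Case mix.** This applies only if emergency patients are in the cohort. With assumed rates of 20% in non-emergency and 50% in emergency patients, the overall rate is 0.9 × 20 + 0.1 × 50 = 23% at a 10% emergency share, and 0.6 × 20 + 0.4 × 50 = 32% at a 40% share. Neither group has changed. With a milder contrast of 20% and 30%, the same change in mix moves it from 21% to 24%.

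**5. Are emergency patients included?** The documents do not settle this. The inclusion criterion refers to patients who had surgery after receiving perioperative TPN. Item 4 gives emergency patients PN in the postoperative period. Item 5 says all patients were operated on from the fifth day of admission onwards. These passages must be reconciled before the cohort, and so the case mix, is defined.

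**The case against.** The strongest reply is that comparison with the literature is ordinary discussion. The plan sets no decision rule and nowhere says that a gap will be called better or worse. That is right: a reader might infer that the plan commits to reading chance as effect, and the text does not support it. It shows only that the comparison could be read that way. Still, the comparison sits in the analysis section, and its input is called the final result.

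A second reply is that the plan is not purely descriptive, since it names chi-square, Fisher's exact and univariate regression. That also stands as far as it goes. But these methods compare groups within the cohort, they are not tied to the external comparison, and a univariate regression does not adjust for case mix.

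Two further readings are tempting and go too far. One is that the plan reports a single pooled figure; it neither requires nor excludes strata, and merely specifies none. The other is that the 7-point precision shows an outcome interval was intended and then dropped; that precision is for malnutrition prevalence.

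Finally, a reader could derive an interval from a proportion and n, or from a mean, SD and n. True, but the plan does not ask for one or use one in the comparison. And an interval deals with chance only: it does nothing for case mix.

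**Conclusion.** The concern holds in this form. No outcome estimate is planned with a confidence interval, and the only contrast outside an all-PN cohort is an unspecified comparison with published studies, so chance and case-mix differences could be read as an effect of PN. At 143 patients and assumed rates of 10% to 40%, an outcome proportion is uncertain by about 5 to 8 points either way. Gaps of 5 points between equally performing studies would be common, and gaps of 10 points would be uncommon but not rare when the rate is near 30% and the published series is small. At a 10% rate a 10-point gap would be rare.

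These sizes rest on assumed rates and comparator sizes, and on the cohort reaching 143. The case-mix illustration rests further on assumed stratum rates and on emergency patients being included. The omission of intervals and of a comparison method does not depend on any of them. The data are not invalidated; what is at risk is the conclusion drawn from them.

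**What to change.** Amend Data Analysis Technique as follows.

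- Report every outcome proportion and every mean with a 95% confidence interval, for example Wilson or exact for proportions. The choice between these is secondary.
- Reconcile the inclusion criterion with Study Procedure items 4 and 5 on whether emergency patients are in the cohort. If both groups are kept, show outcomes separately for emergency and non-emergency patients.
- Show any comparison with a published study as a difference with a 95% interval that uses both sample sizes, and only where outcome definition, follow-up and PN regimen match.
- State that this comparison is descriptive, is not adjusted for case mix, and is not evidence of a PN effect, whether or not the interval excludes zero. Matching on definition, follow-up and regimen still leaves differences in procedure and severity.

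The cost is a few sentences and some extra table columns, with no new data. Results will look less definite, more so by stratum: if 57 of the 143 patients (40%, assumed) were emergencies, a 30% rate in them would carry a half-width of 1.96 × √(0.21/57) = 11.9 points, against 7.5 for the whole cohort. Some published studies may also drop out of the comparison because they do not match.
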